## PROTOCOL SUMMARY

### Study Title

A Phase 2, 24-Week, Randomized, Double-blind, Placebo-controlled, Multicenter Study, With an 80-Week Active Treatment Extension, to Evaluate the Efficacy and Safety of CC-90001 in Subjects With Idiopathic Pulmonary Fibrosis

### Indication

Idiopathic Pulmonary Fibrosis (IPF)

### Objectives

Primary Objective
To evaluate the effect of CC-90001, 200 mg and 400 mg, when orally administered (PO) once daily (QD), compared with placebo, on percent of predicted forced vital capacity (FVC) after 24 weeks of treatment in subjects with IPF.
Secondary Objective(s)
To evaluate the effects of CC-90001, 200 mg and 400 mg PO QD, compared to placebo, after 24 weeks of treatment in subjects with IPF, on: 

• FVC (milliliters [mL])

• Six-minute Walk Test (6MWT)

• Disease progression

• Health-related quality of life: St. George's Respiratory Questionnaire (SGRQ) and University of California San Diego-Shortness of Breath Questionnaire (UCSD-SOBQ)

• Dose response

• Safety and tolerability

 To examine the effect of CC-90001 PO QD, compared to placebo, in subjects with progressive pulmonary fibrosis (PPF), on: 

• Safety and tolerability

### Study Design

This is a Phase 2, multicenter, multinational, double-blind, randomized, placebo-controlled study evaluating the efficacy, safety, [REDACTED] quality of life [REDACTED] [REDACTED] of two oral (PO) treatment doses of CC-90001 (200 mg and 400 mg QD), compared with placebo, for an initial 24 weeks of treatment, in subjects with IPF. This study will also assess the efficacy and long-term safety in the 80-week Active Treatment Extension Phase when all IPF subjects will receive CC-90001 (200 mg or 400 mg PO QD). This study is designed to assess response to treatment by using measures of lung function, disease progression, fibrosis on radiography, and patient-reported outcomes, including cough, dyspnea, and quality of life assessments. It will also assess dose response.

Approximately 165 adult male and female subjects with a diagnosis of IPF (Lynch, 2018) will be randomized 1:1:1 (55 subjects per arm) to treatment with CC-90001 (200 mg or 400 mg PO QD) or matching placebo for an initial 24 weeks. Subjects receiving concurrent protocol-allowable standard of care (SOC) therapy are eligible to participate in the study. Approximately 75 subjects (25 subjects per arm) receiving protocol-allowable SOC are to be enrolled in the study.

The randomization will be stratified based on the concurrent administration of protocol-allowable SOC (Yes/No). Subjects not receiving concurrent protocol-allowable SOC therapy will also be stratified by previous exposure to either pirfenidone or nintedanib (Yes/No).

Subjects completing 24 weeks of treatment will continue onto the 80-week Active Treatment Extension Phase.

Following an initial screening at Visit 1, eligible IPF subjects will be randomized to receive either CC-90001 200 mg or 400 mg PO QD or matching placebo beginning on Day 1 (Baseline [Visit 2]) of the study. At Week 24, all subjects originally randomized to receive placebo will be re-randomized 1:1 to blinded CC-90001 (200 mg or 400 mg PO QD) via interactive web response system (IWRS). All IPF subjects originally randomized to CC-90001 (200 mg or 400 mg PO QD) will remain on that same blinded treatment assignment during the 80-week Active Treatment Extension Phase. During the 80-week Active Treatment Extension Phase, all subjects not receiving concurrent protocol-allowable SOC therapy will have the opportunity, if deemed appropriate by the Investigator, to receive allowed SOC [REDACTED].

An interim analysis will be conducted when approximately 50 non-SOC IPF subjects have completed 24 weeks of treatment. If the safety and efficacy of CC-90001 are favorable, a separate exploratory substudy in subjects with progressive pulmonary fibrosis (PPF) will be initiated. The PPF substudy will enroll non-SOC subjects who do not receive a confirmed IPF diagnosis following central reading of high resolution computed tomography (HRCT) and lung biopsy (if obtained).

The exploratory substudy is a Phase 2, multicenter, multinational, double-blind, randomized, placebo-controlled study evaluating the efficacy, safety, [REDACTED] of one PO treatment dose regimen of CC-90001 (400 mg QD, unless review of benefit-risk favors 200 mg PO QD), compared with placebo, for an initial 24 weeks of treatment, in subjects with PPF. This substudy will also assess the efficacy and long-term safety in the 80-week Active Treatment Extension Phase when all PPF subjects will receive CC-90001. [REDACTED]

[REDACTED] Approximately 45 non-SOC subjects qualifying for enrollment into the substudy will be randomized in a 2:1 ratio to receive CC-90001 or matching placebo for an initial 24 weeks.

All subjects who complete the study treatment phases and those subjects who discontinue investigational product (IP) prior to the completion of the study will participate in the 4-week Post-treatment Observational Follow-up Phase.

To ensure the safety of all subjects in the study, the external Data Monitoring Committee (DMC) and Safety Management Team (SMT) will review safety data as described in the DMC charter and SMT plan. Close monitoring of safety data for all subjects will be conducted throughout the study and will include, but not be limited to, labs, electrocardiograms (ECGs), pulmonary function testing and adverse events.

The study will be conducted in compliance with the International Council for Harmonisation (ICH) of Technical Requirements for Registration of Pharmaceuticals for Human Use/Good Clinical Practice (GCP) and applicable regulatory requirements.

### **Adjudication Committee**

This study will employ an independent adjudication committee that will adjudicate [REDACTED] hospitalizations and deaths. The adjudication committee will determine whether death(s) is associated with respiratory failure [REDACTED]. Details regarding the process and actions of this committee will be described in a separate charter.

### **External Data Monitoring Committee**

Although the Celgene study staff will monitor safety on an ongoing basis throughout the study, formal unblinded safety and efficacy assessments of the study data will be performed by an independent external Data Monitoring Committee (DMC). The DMC is comprised of independent physician experts and a statistician who are not affiliated with the Sponsor and for whom there is no identified conflict of interest. The scope, conduct, membership, processes, and accountabilities of the DMC are specified in the DMC charter.

The DMC will be also responsible for review of the interim analyses data and will make recommendations to a Celgene internal review committee (IRC), who will be responsible for final decision-making. The Celgene IRC members will not play a role in the study conduct and the blind will be maintained for persons responsible for the ongoing conduct and management of the study.

### **Celgene Safety Management Team**

In addition to safety monitoring conducted by Investigators, site study personnel, and the Celgene study team, blinded study safety data will be reviewed by the Celgene SMT. The SMT is comprised of lead representatives from multiple Celgene functions engaged in the CC-90001 development program.

### **Study Population**

The study population includes adult male and female subjects,  $\geq 40$  years of age with a confirmed diagnosis of IPF (Lynch, 2018), percent predicted forced vital capacity (FVC)  $\geq 45\%$  to  $\leq 95\%$ , and hemoglobin-corrected diffusion capacity of the lung for carbon monoxide ( $D_LCO$ )  $\geq 25\%$  to  $\leq 90\%$  predicted at Screening.

### **Length of Study**

The study will have a total duration of up to 116 weeks. The study will consist of an up to 8-week Screening Phase; a 24-week Double-blind Placebo-controlled Treatment Phase; an 80-week Active Treatment Extension Phase; and a 4-week Post-treatment Observational Follow-up Phase.

The End of Trial is defined as either the date of the last visit of the last subject to complete the 4-week Post-treatment Observational Follow-up Phase or the date of receipt of the last data point from the last subject that is required for primary, secondary [REDACTED] analysis, as prespecified in the protocol (whichever is the later date).

## Study Treatments

The IPF study subjects are provided with the following IP treatments:

- 24-Week Double-blind Placebo-controlled Treatment Phase: Baseline (Visit 2) to Week 24
  - CC-90001 400 mg PO QD
  - CC-90001 200 mg PO QD
  - Placebo PO QD
- 80-Week Active Treatment Extension Phase: Week 24 + 1 day to Week 104
  - CC-90001 400 mg PO QD
  - CC-90001 200 mg PO QD

The PPF substudy subjects are provided with the following IP treatments:

- 24-Week Double-blind Placebo-controlled Treatment Phase: Baseline (Visit 2) to Week 24
  - CC-90001 (400 mg PO QD, unless review of benefit-risk favors 200 mg PO QD)
  - Placebo PO QD
- 80-Week Active Treatment Extension Phase: Week 24 + 1 day to Week 104
  - CC-90001 (400 mg PO QD, unless review of benefit-risk favors 200 mg PO QD)

## Overview of Key Efficacy Assessments

- Pulmonary Function Tests
  - FVC
  - DLCO
  - Arterial oxygen saturation by pulse oximetry (SpO2)

- 6-minute Walk Test (6MWT) including Borg Scale Assessment

- Disease Progression

- Patient-reported Outcomes
  - St. George's Respiratory Questionnaire (SGRQ)

- University of California San Diego Shortness of Breath Questionnaire (UCSD-SOBQ)

**Overview of Key Safety Assessments**

- Adverse events
- Physical examination, vital signs, and weight
- Clinical laboratory tests including hematology, chemistry, and urinalysis (including urine cytology)
- 12-lead electrocardiogram
- Pregnancy testing and pregnancy education

### Statistical Methods

The primary objective of the study is to estimate the effect of CC-90001 in subjects with IPF either not receiving SOC or currently receiving SOC.

Approximately 165 subjects (55 subjects for CC-90001 200 mg with or without [±] SOC, 55 subjects for CC-90001 400 mg ± SOC, and 55 subjects for placebo ± SOC) provide 75% power for testing an overall difference of 2.2 percentage points or more in the Week 24 mean change from Baseline of percent predicted FVC value between either active treatment group ± SOC and the placebo group ± SOC (two-sided t-test;  $\alpha = 0.1$ ; standard deviation [SD] = 5%), assuming that approximately 45% of subjects will be receiving concurrent protocol-allowable SOC based on the projected enrollment. The group size estimate is based on an assumed treatment difference of 3 in percent predicted FVC in the non-SOC cohort and 1.3 in percent predicted FVC in the SOC cohort at Week 24 from Baseline. The study will also estimate the effect of CC-90001 in the PPF cohort.

## 1. INTRODUCTION

### 1.1. Disease Background

#### 1.1.1. Idiopathic Pulmonary Fibrosis

Idiopathic pulmonary fibrosis (IPF) is a chronic, progressive and often lethal fibrosing interstitial lung disease of unknown etiology characterized by a poor prognosis (Raghu, 2011).

The reported prevalence of IPF varies geographically; for example, the published prevalence of IPF per 100,000 people ranges from 13-63 in the United States of America (USA) and from 3-23 in Europe (Ley, 2013). Approximately half of IPF patients either die or undergo lung transplantation within 3 to 5 years of diagnosis (Ley, 2013). The disease typically occurs in people between the ages of 40 and 70 years (median age is 66 years) and affects men more frequently than women. Most patients are former smokers. There are no proven risk factors for IPF, but < 5% of patients have a family history of interstitial lung disease (Raghu, 2011).

The diagnosis of IPF is made after excluding other conditions associated with pulmonary fibrosis and is based on a characteristic clinical presentation, radiographic features, and sometimes pathologic specimens (Raghu, 2011). The diagnosis of IPF requires information from several sources to be interpreted and integrated, and this can pose significant challenges in patient selection for this trial. Since the publication of the 2011 ATS/ERS guidelines (Raghu, 2011), diagnosing IPF continues to evolve through ongoing research and clinical experience. Very recently, a Fleischner Society White paper on the diagnostic criteria of IPF was published (Lynch, 2018). In this paper, a new category in the interpretation of high resolution computed tomography (HRCT) patterns, “computed tomography (CT) pattern indeterminate for usual interstitial pneumonia (UIP),” was proposed to encompass an HRCT that may be consistent with IPF and that lacks features most consistent with a non-IPF diagnosis. This new category can be considered a refinement of the 2011 ATS/ERS criteria, in which an HRCT classified as “inconsistent with UIP” did not distinguish between patients whose scans were insufficient to secure this diagnosis in the absence of additional information (eg, lung biopsy), from patients who were unlikely to have IPF.

IPF is characterized by interstitial fibrosis, which typically results in chronic irreversible scarring. These pathological changes are associated with a progressive decline in pulmonary function, which may lead to respiratory failure and death; some patients may experience episodes of acute respiratory worsening despite previous stability (Raghu, 2011).

The precise biological basis of IPF remains unclear. Over a lifetime, the lungs are exposed to repetitive injury from a variety of exogenous and endogenous stimuli. Several local and systemic factors (eg, fibroblasts, circulating fibrocytes, chemokines, growth factors, and clotting factors) contribute to tissue healing and functional recovery. Dysregulation of this intricate network, through genetic predisposition, autoimmune conditions, or superimposed diseases are proposed to lead to aberrant wound healing that may culminate in pulmonary fibrosis. Alternatively, excessive injury to the lung may overwhelm reparative mechanisms and may lead to pulmonary fibrosis (Nicholson, 2002; King, 2001).

In the recent past, the pharmacological treatment of IPF has changed considerably. Two approved treatments, pirfenidone and nintedanib, both appear to have modest effects on

progression-free survival and decline in pulmonary function (Noble, 2011; King, 2014; Richeldi, 2014). To date, lung transplantation has been shown to improve mortality in carefully selected patients (Kistler, 2014). Despite these advances, there remains a large unmet need for a safe and effective therapy for IPF that delays disease progression, improves pulmonary function, and reduces the mortality rate.

### 1.1.2. Progressive Forms of Pulmonary Fibrosis Other Than IPF

Besides IPF, other interstitial lung diseases (ILDs) can manifest as a progressive fibrosing phenotype (Wells, 2018; Cottin, 2018). The chest HRCT appearance in such individuals is variable and may conform to a UIP pattern similar to that in patients with IPF but can also be distinctive and be described as “indeterminate” for UIP or most consistent with a non-IPF diagnosis. Such cases would represent a radiological subset of “progressive-fibrosing ILD,” a recently described term that recognizes the progressive nature of such ILDs (Flaherty, 2017; Cottin, 2018). Progressive fibrosis of the lung parenchyma causes progressive deterioration in lung function, respiratory symptoms and quality of life and therefore increases the risk of early death (Olson, 2016; Cottin, 2018).

## 1.2. Compound Background

[figure not shown]
[REDACTED]

[REDACTED]

CC-90001 is a potent inhibitor of JN [REDACTED]

[figure not shown]
[REDACTED]

[figure not shown]

## 1.6. Rationale

### 1.6.1. Study Rationale and Purpose

Most treatment strategies for fibrotic disorders like IPF have been based on eliminating or suppressing the inflammatory factors involved in the disease with immunosuppressive drugs, such as corticosteroids and cytotoxic agents. Although these drugs may reduce the inflammatory cascade by blocking the proliferation of cells and the recruitment of inflammatory leukocytes, or by killing recruited cells, these drugs do not necessarily target the underlying fibrotic response well, which typically involves both local cells (stromal cells) and recruited cells (inflammatory leukocytes) (Wynn, 2004). By inhibiting JNK, CC-90001 is hypothesized to interrupt both areas of this process. More recently, two pharmacological therapies, pirfenidone and nintedanib, commercially available in some regions of the world, have demonstrated modest effects on progression-free survival and decline in pulmonary function in patients with IPF (Noble, 2011; King, 2014; Richeldi, 2014). The relatively modest benefits associated with these agents for a disease as serious as IPF indicate that there remains an important, unmet need in the treatment of IPF. Based on recent insights into the pathogenesis of IPF, the underlying rationale for the current protocol is that JNK plays a pivotal role in the progression of pulmonary fibrosis and that inhibition of JNK, by CC-90001, will lead to improved lung function and other outcomes in patients with IPF.

### 1.6.2. Rationale for the Study Design

The Phase 3 pirfenidone and nintedanib trials demonstrated benefits on FVC in patients receiving active treatment, compared with placebo, after 52 weeks (King, 2014; Richeldi, 2014) and 72 weeks (Noble, 2011) of treatment, respectively. Apparent benefits in FVC were observed as early as 24 weeks following onset of treatment (Noble, 2011; King, 2014; Richeldi, 2014). Therefore, it is anticipated that a treatment response with CC-90001 in IPF should occur as early as 24 weeks after initiation of treatment, especially if the effect is robust. The 24-week Double-blind Placebo-controlled Treatment Phase should provide the shortest study duration to reasonably assess the efficacy and safety of CC-90001 with or without ( $\pm$ ) standard of care (SOC) in IPF subjects. The 80-week Active Treatment Extension Phase will provide additional [REDACTED] long-term safety and efficacy information for CC-90001  $\pm$  SOC. It will also provide those subjects randomized to the placebo treatment without SOC the opportunity to receive active CC-90001 (200 mg or 400 mg PO QD).

### 1.6.3. Rationale for Selecting FVC as the Primary Endpoint

Change in FVC was selected as the primary endpoint because of its widespread clinical use and the clinical relevance of irreversible loss of lung function. Change in FVC is currently accepted by health authorities as a primary endpoint in IPF trials in part because it is a reliable, responsive

measurement. Deterioration in FVC  $\geq$  10% from baseline over 6 months has been shown to predict mortality in IPF patients (du Bois, 2011).

#### 1.6.4. Rationale for Dose, Schedule and Regimen Selection

The 200 mg and 400 mg QD doses of CC-90001 were selected based on preclinical and clinical data in addition to simulation that supports adequate target engagement at clinically tolerated doses with sufficient PK distribution between doses. Additionally, exposures in this dose range are consistent with exposures required for efficacy in preclinical models.

##### 1.6.4.1. Biological Activity

[Redacted] CC-930, a JNK inhibitor, was previously evaluated for activity in both UVB-induced phospho-c-Jun expression in healthy volunteers, and for safety in IPF subjects. In IPF subjects treated with CC-930, a dose-dependent trend in reducing plasma MMP-7 was observed, and changes in plasma MMP-7, SP-A, SP-D, and TNC levels significantly correlated with changes in FVC (Schafer, 2013; van der Velden, 2016). [Redacted]

[Redacted] Thus, the 200 and 400 mg doses

[figure not shown]

of CC-90001, which significantly inhibited the JNK pathway [REDACTED], phospho-c-Jun, are in a range that is expected to have an effect on the IPF [REDACTED].

### 1.6.5. Rationale for Placebo Comparator

A placebo control is needed in this Phase 2 trial to accurately determine the clinical benefits and safety profile of CC-90001.

The study embodies neither expectation nor intent that patients discontinue indicated and well-tolerated treatment to participate. Although both pirfenidone and nintedanib have demonstrated clinical benefits compared to placebo, these benefits have been modest and variable; many patients receiving these medications may fail to demonstrate clinically meaningful benefits and/or may experience significant tolerability issues or adverse reactions that limit their clinical utility. Clinical experience with CC-90001 thus far suggests that gastrointestinal-related AEs may occur in IPF, similar to those that occur following administration of pirfenidone and nintedanib. After Week 24 of this study, all subjects will be given the opportunity to receive CC-90001 (200 mg or 400 mg PO QD). In addition, if deemed appropriate by the Investigator, all subjects not receiving concurrent protocol-allowable SOC therapy will be permitted to receive allowed SOC [REDACTED].

**1.6.7. Rationale for Patient-Reported Outcomes**

In chronic, progressive and ultimately fatal diseases like IPF, assessment of health-related quality of life is especially useful in providing the patients' perspective on treatment benefit. These instruments are used to directly measure treatment benefit that is of greatest relevance to the patient. Patient-reported outcome instruments have been included in this study to document the effect of CC-90001 on symptoms and quality of life.

This study will implement three patient-reported outcomes, SGRQ, [REDACTED] and UCSD-SOBQ, to obtain preliminary information that will inform on which tools to use in the Phase 3 program. The SGRQ has been chosen as it has demonstrated acceptable psychometric characteristics in patients with IPF, including construct validity, reliability, and ability to detect change over time (Yorke, 2010; Swigris, 2010). [REDACTED]

SGRQ

possess reasonable validity for differentiating subjects whose IPF disease severity changes over time (Swigris, 2010). The UCSD-SOBQ demonstrates content validity (Gries, 2013) and is able to detect changes in symptoms over time (Gries, 2013; Swigris, 2012) in patients with IPF (Swigris, 2012a).

## 1.7. Potential Risks of CC-90001 and the Study Population

Based on the Phase 1 studies in healthy subjects and the Phase 1b study in pulmonary fibrosis subjects, the TEAEs associated with administration of CC-90001 are mostly gastrointestinal in nature. Gastrointestinal TEAEs reported in these studies included nausea, diarrhea, indigestion, abdominal discomfort/cramping, emesis, and constipation. Headache, rash, dermatitis, fatigue and musculoskeletal pain TEAEs were also reported. The majority of the reported TEAEs were mild or moderate in severity. Some subjects who experienced nausea in the Phase 1 studies have reported less nausea when the IP was taken with food. There were no SAEs reported in the Phase 1 studies.

The Sponsor has instituted extensive safety monitoring into this protocol based upon potential risks associated with CC-90001 and the disease under study.

- Frequent study visits to assess safety laboratory results, including, but not limited to, liver function, white blood cell (WBC) count, hemoglobin, total cholesterol, high density lipoprotein (HDL), low density lipoprotein (LDL), triglycerides, pulmonary function and arterial oxygen saturation (SpO2).
- Individual subject dose stopping rules and study stopping rules to ensure subjects are discontinued from CC-90001 in the event of severe liver toxicity. In a study conducted with the structurally unrelated pan-JNK inhibitor, CC-930, IPF subjects treated with high doses of CC-930 demonstrated abnormal liver function tests after approximately 8-12 weeks of daily dosing. In order to support this Phase 2 study with chronic dosing, the CC-90001-CP-003 study in pulmonary fibrosis subjects was conducted to understand the safety profile after a 12-week treatment duration.
- CC-90001 may be an inhibitor of liver transporters (eg, OATP1B1 and OATP1B3) and breast cancer resistance protein (BCRP). Therefore, subjects taking statins

concomitantly with CC-90001 may experience increased plasma concentrations of statins with prescribed doses. To ensure the safety of the subjects, concomitant statins will be dose adjusted to a therapeutic level (see Section 8.2.1).

- Urine cytology to examine for abnormal cellular findings.
- Electrocardiograms (ECGs) with centralized over-read and blood pressure measurements will be performed to monitor for potential cardiovascular effects.
- Required and frequent Investigator/Celgene safety review meetings to ensure appropriate and timely intervention (such as study discontinuation) in the event that a safety signal is identified.

Celgene is confident that the safety monitoring plan included within this protocol is sufficient to monitor for potential safety risks of CC-90001. In addition, provisions for monitoring for disease-specific complications, such as hypoxemia and decline in pulmonary function secondary to disease progression, have also been included as part of the protocol design.

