  - Chemistry panel will include albumin, alanine aminotransferase (ALT; serum glutamic pyruvic transaminase [SGPT]), alkaline phosphatase, aspartate aminotransferase (AST; serum glutamic oxaloacetic transaminase [SGOT]), gamma-glutamyl transferase (GGT), bicarbonate, blood urea nitrogen, calcium, chloride, creatinine, glucose, lactate dehydrogenase, magnesium, phosphorus, potassium, sodium, total bilirubin, direct bilirubin, indirect bilirubin, total cholesterol, HDL, LDL, total protein, triglycerides, and uric acid.
  - Prothrombin time (PT) and international normalized ratio (INR) will be obtained only in those subjects receiving vitamin K antagonists (eg, warfarin).

- Urinalysis: semiquantitative testing via dipstick (specific gravity, pH, glucose, erythrocytes, leukocytes, protein, and nitrite) will be performed by the central laboratory. Microscopic urinalysis (epithelial cells, RBC, WBC, and casts) will be performed only if the dipstick urinalysis is abnormal.

*Note: If the Screening Visit 1 urinalysis test results are positive (eg, leukocyte esterase or nitrite present), a urine culture test is required and the subject must have a confirmatory negative urine culture test to rule out urinary tract infection (UTI) prior to randomization, which can be performed using the provided central laboratory urine culture kits or a local laboratory at the site.*

- In addition to the routine urinalysis, urine cytology will be done for the detection of abnormal cells. The urine cytology specimen will be evaluated by a pathologist at the central laboratory.

*Note: “Abnormal, clinically significant” results should be recorded in the Medical History CRF if found prior to first dose of IP, or in the AE CRF if found after the first dose of IP. Clinical laboratory evaluations do not require subjects to be fasting. However, the site will record on the lab requisition form whether a clinical laboratory evaluation was obtained in the fasting or nonfasting state.*

- Mycobacterium tuberculosis (TB) testing: Testing will be done at the Screening Visit via QuantiFERON®-TB Gold.

*Note: A positive QuantiFERON-TB Gold test or 2 successive indeterminate QuantiFERON-TB Gold tests will disqualify the subject from further participation in the study.*

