### 8.2.1. Statins

Due to the potential for DDIs, the following must be done to ensure the safety of subjects taking statins while on the study:

- During the Screening phase of the study, all subjects receiving statins should be prescribed the lowest approved statin dose for adults approximately 1 week before Visit 2 (Baseline). For example, a subject receiving atorvastatin 20 mg during the Screening Period should be instructed to begin taking atorvastatin 10 mg, instead, approximately 1 week prior to randomization.

*Note: Subjects who are already receiving the lowest approved statin dose for adults should remain on that dose.*

- At Visit 2 (Baseline), eligible subjects will begin treatment with CC-90001. Following multiple oral doses of CC-90001, the steady state should be achieved on approximately Day 5.
- At Visit 3, the lipid profile will be assessed. Based on results of the subjects' lipid profile at Visit 3, the statin dose may be increased to the next highest approved dose, if indicated.

*Note: If the lipid profile at Visit 3 is comparable to the lipid profile from Visit 1 (Screening), the statin dose should not be increased.*

- At Visit 4, the lipid profile will be assessed. Based on the subjects' lipid profile at Visit 4, the statin dose may be increased to the next approved dose, if indicated.

*Note: If the lipid profile at Visit 4 is comparable to the lipid profile from Visit 1 (Screening), the statin dose should not be increased.*

The Investigator should use his/her clinical judgement to decide when/if the further increase in the statin dose is warranted and how to assess these subjects. **In particular, Investigators should monitor closely for AEs associated with increased statin exposures (eg, myalgia, liver function test abnormalities).** If needed, the Investigator should refer the subject to his/her general practitioner or other appropriate healthcare provider for further follow-up.

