### 9.7. Safety Analysis

The safety analyses for the 24-week Double-blind Placebo-controlled Treatment Phase will be performed using the safety population as defined in Section 9.2 by treatment group. The safety analyses will also be performed for the CC-90001 exposure period for subjects who receive at least one dose of CC-90001, which will include safety data during the 24-week Double-blind Placebo-controlled Treatment Phase and the 80-week Active Treatment Extension Phase. Safety will be assessed by clinical review of all relevant parameters including AEs, laboratory tests, vital signs, and ECG measurements; summary of safety parameters will include data collected at scheduled, unscheduled, and early termination visit, and post-treatment observational follow-up visit. No inferential testing for statistical significance will be performed.

Adverse events will be classified using the MedDRA classification system. All AEs will be summarized by frequency, severity and relationship to IP. Adverse events leading to death or to discontinuation from treatment and serious adverse events will be listed separately. Study drug-related AEs will be listed separately. In the by-subject analysis, a subject having the same event more than once will be counted only once and by greatest severity.

Laboratory data will be summarized by visit descriptively (count, mean, median, standard deviation, and range). In addition, shift tables showing the number of subjects with values below, within and above the normal ranges pretreatment versus post treatment, together with the number determined to be clinically significant, will be provided.

Vital sign measurements, including weight, will be summarized descriptively by visit (count, mean, median, standard deviation, and range).

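### Section 9.7 never uses the fasting state that sites record, so meal effects on triglycerides and glucose stay mixed into the laboratory summaries and shift tables (minor)

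*Combined protocol and SAP*

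**What the plan says.** Section 1.7 lists, among the laboratory results followed at frequent visits because of potential risks of the drug and the disease, "hemoglobin, total cholesterol, high density lipoprotein (HDL), low density lipoprotein (LDL), triglycerides". Section 6.1 places the same lipids in the chemistry panel ("total cholesterol, HDL, LDL, total protein, triglycerides, and uric acid"), along with glucose ("calcium, chloride, creatinine, glucose, lactate dehydrogenase"). Glucose is not named in Section 1.7.

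On meals, Section 6.1 states "Clinical laboratory evaluations do not require subjects to be fasting", and adds that "the site will record on the lab requisition form whether a clinical laboratory evaluation was obtained in the fasting or nonfasting state".

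Section 9.7 is the only description of laboratory analysis: "Laboratory data will be summarized by visit descriptively (count, mean, median, standard deviation, and range". It adds "shift tables showing the number of subjects with values below, within and above the normal ranges pretreatment versus post treatment", with the number judged clinically significant. These analyses are done by treatment group for the 24-week phase. They are also done over the CC-90001 exposure period, which joins the 24-week phase to the 80-week extension. Unscheduled, early-termination and follow-up values are included. No inferential testing is planned. The recorded fasting state is not used to split, restrict or flag anything.

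**The concern.** The sponsor collects the one variable needed to separate a meal effect from a drug effect, and the stated analysis leaves it out. Triglycerides and glucose depend on recent food. So does LDL if it is calculated from the other lipids, but Section 6.1 does not say how LDL is obtained.

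Two consequences follow. A by-visit mean or SD for these analytes mixes two states. A shift table may classify a subject from a fasting sample before treatment and a nonfasting one after it, or the reverse, and so record a move across the normal limit that owes nothing to CC-90001, or miss one that does. Safety and tolerability is a secondary objective of the IPF study and of the PPF substudy, and these lipids are ones the protocol itself picks out.

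**Working it through.** The plan states no figure that bears on this point, so there is none to reproduce. The check has a textual part and an illustration under assumptions.

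**Text side by side**

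| Question | Section | Answer |
|---|---|---|
| Is fasting required? | 6.1 | No |
| Is the state recorded? | 6.1 | Yes, on the laboratory requisition form |
| Do summaries or shift tables use it? | 9.7 | Not mentioned |
| Are draws fixed relative to dosing? | 6.2 | Before dosing on the visit day |
| Are draws fixed relative to meals? | 6.1, 6.2 | No |
| Is there a concurrent placebo up to Week 24? | 3.1 | Yes: randomized 1:1:1, blinded, 55 per arm |
| Is there a concurrent placebo in the extension? | 3.1 | No: all IPF subjects receive CC-90001 |

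**Illustration.** The documents give neither the meal effect nor the nonfasting share. Assume a meal shift *m* of 0.25 to 1.0 within-state SD and a nonfasting share *q* of 20% to 80%.

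1. *Noise in a by-visit summary.* The SD is inflated by √(1 + q(1−q)m²).
   - Smallest (q = 0.2 or 0.8, m = 0.25): √(1 + 0.16 × 0.0625) = 1.005.
   - Largest (q = 0.5, m = 1.0): √(1 + 0.25 × 1) = 1.118.
   - The SD therefore rises by 0.5% to 12%.

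2. *Chance imbalance between two randomized arms of 55.* The SD of the difference in nonfasting share is √(2q(1−q)/55).
   - q = 0.2 or 0.8: 0.076. q = 0.5: 0.095. That is 7.6 to 9.5 percentage points.
   - At 1.96 SDs, the spurious arm difference runs from 1.96 × 0.076 × 0.25 = 0.04 SD to 1.96 × 0.095 × 1.0 = 0.19 SD. Its expectation is zero.

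3. *Mismatched pairs in a shift table.* If a subject's states at the two times are independent with equal share *q*, the mismatched fraction is 2q(1−q): 32% at q = 0.2 or 0.8, and 50% at q = 0.5. It is lower if subjects keep to one habit.
   - The excess of fasting-then-nonfasting pairs over the reverse equals q(post) − q(pre), whatever the within-subject correlation. With equal shares, false shifts go both ways. They lean one way only if the share drifts.

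4. *Drift over time.* The spurious movement of a mean is (change in q) × m. For an assumed drift of 10 to 30 points it runs from 0.10 × 0.25 = 0.025 SD to 0.30 × 1.0 = 0.30 SD. Up to Week 24 a drift common to all arms is visible in the placebo arm; in the extension no concurrent control shows it. Nothing in the documents indicates that such a drift will occur.

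**The case against.** The strongest reply is that Section 9.1 presents Section 9 as an outline and defers detail to a separate SAP. A fasting column is SAP-level detail, so the gap is inferred from silence. That stands as a limit on the claim, but no SAP text in the combined document closes the gap. It is also fair that laboratory output is purely descriptive, that the shift tables carry a count of clinically significant values, and that morning lung-function testing within one hour of a fixed time (Section 6.4.1.1) makes a consistent fasting state within a subject more likely. All of this keeps the point small.

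Three stronger readings are tempting and are not supported.

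- *Bias between arms.* A reader might infer that subjects on active drug eat more before visits, because Section 1.7 reports less nausea when dosing with food. Section 6.2 puts visit-day evaluations before dosing, so food taken with that dose should follow the draw. The first 24 weeks are also randomized and blinded. No systematic gap in fasting share is shown.
- *Inflated variance of change from Baseline.* Section 9.7 specifies no change-from-Baseline table for laboratory data, so a variance figure for such a change would criticize an analysis the plan does not state.
- *A conflict with Section 8.2.1.* That section says "If the lipid profile at Visit 3 is comparable to the lipid profile from Visit 1 (Screening), the statin dose should not be increased" and does not mention fasting state. It does not contradict Section 6.1, and it governs statin dosing, not analysis. No change to it is asked for.

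**Conclusion.** The point holds as a minor gap in the safety analysis. Fasting state is recorded and, on the text available, not used. In the 24-week phase the cost is noise and chance imbalance. The more exposed outputs are the pretreatment-versus-post-treatment shift tables, above all over the CC-90001 exposure period, because the extension has no placebo group to reveal a change in meal habits.

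The size cannot be derived from the documents. The ranges under the working rest on an assumed meal effect, nonfasting share and drift, and run from negligible to noticeable. The case is clearest for triglycerides and glucose; for LDL it depends on how LDL is measured. The primary endpoint, sample size and interim analyses are not affected.

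**What to change.** In Section 9.7, or in the SAP it relies on:

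- Carry the fasting flag from the requisition form into the analysis data.
- For triglycerides, LDL and glucose, add by-visit summaries and shift tables split by recorded fasting state. Base the added shifts on pairs of samples in the same state, as a supplement to the all-draws tables.
- Report the share of fasting draws by arm and visit, so that a reader can see whether drift or imbalance occurred.

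The cost is a few extra tables and one data-transfer field, with no new samples or visits. Same-state shift tables will have smaller counts: under independence with half the draws nonfasting, 0.5 × 55 ≈ 28 pairs per arm, and with 20% or 80% nonfasting, 0.68 × 55 ≈ 37. That is why the all-draws tables should stay. The split will not separate the effect of statin dose changes on lipids, which is a different source of confounding.
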